G*power 3.1 power analysis software (Heinrich-Heine-University, Düsseldorf, Germany) estimated the minimum total sample size ($N=140$) given the critical $F_{(3, 136)}=2.67$, an effect size $f=0.14$ (partial $\eta^2=0.02$), $p=0.05$, $1-\beta=0.80$, groups=4, time points=2, and correlation among the measurements=0.50. The authors presented data as means and 95% confidence intervals [95% CIs]. The Kolmogorov-Smirnov, Leven's, Box's, and Mauchly's tests confirmed the assumptions of normality, homogeneity of variances and covariances, and sphericity, respectively. General linear models (twelve separate 2x4 mixed-design analyses of covariances for each PS measure) estimated whether mean changes [95% CIs] in PS measure from initial to final testing depended on whether participants received the DNS, VIBRO, and MIX exercise program or did not (CONTROL) after controlling for mean-centered BMI (Cibulková et al., 2022; Hue et al., 2007). Following the time-by-group interaction effects, which revealed whether estimated changes over time depended on the participants' group (i.e., differed at least between one group-comparison pair), we computed simple effects tests to estimate mean changes over time (mean difference from initial to final testing) within the groups. The follow-up investigation proceeded with contrast analysis, which assessed the degree to which estimated mean changes of PS measures differed between the group-comparison pairs. The authors calculated the effect size for time-by-group interaction effects and simple effects using partial eta squared (partial η^2 : 0.01 small; 0.06 medium; 0.14 large) (Cohen, 2013) and Hedge's g average (Hedge's s_{av} : $<|0.20|$ trivial; $|0.20|$ small; $|0.50|$ medium; $|0.80|$ large) (Lakens, 2013), respectively. The Bonferroni test corrected p-values and 95% CI; the alpha level was $p\leq0.05$. We used SPSS version 23.0 (SPSS Inc., Chicago, IL, USA) and GraphPad Prism version 8.0 (GraphPad Software, San Diego, California, USA) to analyse and plot the data, respectively.

References

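### Uncorrected partial eta squared, graded small from 0.01, averages about 0.017 for an interaction with no effect, so the label alone cannot tell a small effect from none (minor)

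*Protocol*

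**What the plan says.** All of this is in the Statistical analyses section of the Protocol, except the group sizes, which are under Participants.

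- Twelve separate 2x4 mixed analyses of covariance are planned, one per postural stability measure, each adjusted for mean-centred BMI.
- On effect sizes: "The authors calculated the effect size for time-by-group interaction effects and simple effects using partial eta squared", followed by Hedges' g. The sentence ends by pairing the two lists in order, so partial eta squared belongs to the interactions and Hedges' g to the simple effects.
- The grades for partial eta squared are "0.01 small; 0.06 medium; 0.14 large". Those for Hedges' g are "trivial; $|0.20|$ small; $|0.50|$ medium; $|0.80|$ large", so only Hedges' g has a band below small.
- Decisions rest on tests: "The Bonferroni test corrected p-values and 95% CI; the alpha level was $p\leq0.05".
- The section states no bias correction or confidence interval for partial eta squared. It does not say whether the grades apply to non-significant interactions.

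**The concern.** The grades are benchmarks for the size of a population effect, but they are applied to a sample statistic that is never negative and is biased upward. For an interaction with three numerator degrees of freedom and a sample of this size, the bias alone may exceed the lowest cut-off of 0.01. A reader who sees a value of 0.015 graded small would take it as information about size, although such a value is typical when the programmes do not differ at all. With twelve measures, several such labels can be expected by chance, and real effects would look somewhat larger than they are.

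**Working it through.** **The plan's own figure.** Inputs: "estimated the minimum total sample size ($N=140", "critical $F_{(3, 136)}=2.67", "an effect size $f=0.14$ (partial $\eta^2=0.02", power 0.80 and "groups=4, time points=2, and correlation among the measurements=0.50". For a within-between interaction, df1 = 3, df2 = N − 4 and λ = f²·N·m/(1 − ρ), with m = 2 and ρ = 0.50.

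- The critical F(3,136) is 2.671, as stated.
- With f² = 0.02/0.98 (f = 0.1429), λ = 11.43 and power at N = 140 is 0.808. The minimum N is 138, or 140 with equal groups.
- With f rounded to 0.14, power is 0.790 and the minimum N is 144.

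The stated figure is reproduced within rounding, and the sample size is not in question here.

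**Degrees of freedom in the analysis.** The final groups are 45 + 45 + 44 + 43 = 177 (the text gives a total of 180). Four groups and one covariate leave df2 = 177 − 4 − 1 = 172. This is inferred; the Protocol prints only 136.

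**Distribution with no effect.** Partial eta squared = 3F/(3F + df2), which follows Beta(3/2, df2/2) under the usual model assumptions. Its mean is 3/(3 + df2).

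| Basis | df2 | Mean with no effect | P(at least 0.01) |
|---|---|---|---|
| 140, planned, no covariate | 136 | 0.0216 | 0.71 |
| 177, BMI | 172 | 0.0171 | 0.63 |
| 180, BMI | 175 | 0.0169 | 0.62 |
| 230, BMI | 225 | 0.0132 | 0.52 |

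At df2 = 172 the median is 0.0136, so both mean and median lie above 0.01. If none of the twelve measures had an effect, 12 × 0.629 = 7.6 values of at least 0.01 would be expected.

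**Relation to the test.** At df (3,172) the critical F is 2.657. This corresponds to a partial eta squared of 3 × 2.657/(3 × 2.657 + 172) = 0.044. Values from 0.01 up to 0.044 are therefore not significant even before any Bonferroni correction. With no effect they make up 0.63 − 0.05 = 0.58 of cases.

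**Bias with a real effect.** Simulation from the noncentral F with N = 177 and λ = N·η²/(1 − η²), where η² is the true value:

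| True value | Mean partial eta squared | Mean partial omega squared, not truncated |
|---|---|---|
| 0 | 0.017 | 0.000 |
| 0.02 | 0.037 | 0.020 |
| 0.06 | 0.076 | 0.059 |

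Here 0.02 is on the scale of the reported statistic. The power calculation multiplies f² by m/(1 − ρ) = 4, so this row is an illustration and not the planned effect.

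**What a correction achieves.** Partial omega squared is 3(F − 1)/(3(F − 1) + N). With no effect it still reaches 0.01 in about 19% of cases. If negative values are shown as 0, its mean with no effect is about 0.005 rather than 0.000.

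**The case against.** A reader might infer that about 63% of interactions with no effect would be reported as effects. The documents do not support that. The grades describe size and are not a decision rule; the interaction is tested by F at the 5% level, and the error rate stays at 5% per test. A partial eta squared of exactly 0.01 at df (3,172) has p = 0.63, so a reader who sees the p-value beside the label is not misled about significance.

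Three further objections have weight.

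- The Protocol does not say that a verbal grade is attached to non-significant interactions. The count of 7.6 out of twelve is the expected number of values at or above 0.01, and a forecast of wording only if every value is graded.
- Partial eta squared is not the main measure of how the programmes differ. That role falls to the contrasts between groups and the mean changes with 95% confidence intervals, which this bias does not touch.
- The measure and its cut-offs are a common convention, and changing the estimator does not remove the problem entirely, as the 19% above shows.

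These points lower the severity but leave the bias in place. The Protocol fixes an uncorrected statistic as the interaction effect size, and with no effect its average exceeds the first cut-off at every sample size considered.

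**Conclusion.** The point holds as a minor weakness in reporting. At N = 177 the interaction effect size is overstated by about 0.016 to 0.017, which is more than the 0.01 at which the small grade starts. That grade alone cannot separate a small effect from none.

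The exact figures rest on the inferred df2 of 172 and on the model assumptions behind the F test. The conclusion does not depend on which sample is analysed: the probability of reaching 0.01 with no effect runs from 52% (230 analysed) to 71% (140 analysed). No test, p-value, contrast or confidence interval in the plan is made wrong by this.

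**What to change.** In the Statistical analyses section, report partial omega squared, 3(F − 1)/(3(F − 1) + N), for each interaction, in place of partial eta squared or beside it. Add a confidence interval obtained from the noncentral F by converting the limits for λ with λ/(λ + N). State whether negative estimates are shown as 0. Add one sentence saying that a size grade is not read as evidence of an effect where the interaction is not significant. That sentence is needed because the corrected measure alone still passes 0.01 in about one in five cases with no effect.

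The cost is small: F, its degrees of freedom and N are available from the planned analyses, and no test or sample size changes. The drawbacks are slightly smaller reported effect sizes and less direct comparison with papers that report partial eta squared. Showing both measures avoids the second.
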